UHAS	University of Health and Allied Sciences
UNID	Unique Study Identification Number
VF	Visual Field
WHO	World Health Organization

1 PROTOCOL SUMMARY

Study Title:	Safety and efficacy of triple drug therapy for individuals infected with Onchocerca volvulus
Type of Study:	Open label, randomized clinical trial
Study Drugs:	Diethylcarbamazine citrate (DEC) tablets - C ₁₆ H ₂₉ N ₃ O ₈ Ivermectin tablets - C ₄₈ H ₇₄ O ₁₄ Albendazole tablets - C ₁₂ H ₁₅ N ₃ O ₂ S
Population:	Participants from the study ‘ Microfilarial Clearance from the Eye and Ocular Changes Associated with Ivermectin Treatment in Individuals with Onchocerciasis ’ will be invited to participate in the study described in this protocol. These participants were recruited from the Nkwanta North District in the Volta region of Ghana located at the northeastern part of Ghana. The population of Nkwanta North District, according to the 2010 Population and Housing Census, is 64,553.
Number of Participants:	Up to 300 eligible participants
Study Duration	24 months
Duration of Participant Participation	Participants will be followed for 18 months after their first treatment.
Primary Objectives:	Safety: To compare rates and types of severe adverse events (grade 3 or higher) that occur within 7 days following 1 day or 3 days of triple drug treatment (DEC with ivermectin and albendazole; “IDA”) with the comparator regimen of 1 day of treatment with ivermectin and albendazole in persons with onchocerciasis at least six months after pretreatment with ivermectin alone (in a preceding study). Efficacy: To compare the effect of three treatment regimens for killing or sterilizing adult female O. volvulus worms based on the percentage of all adult female worms in nodules that are alive with embryos in the uterus 18 months after treatment.

Secondary Objectives:	Safety: 
 1. To compare rates of adverse events grade 3 or higher by treatment group that occur within 7 days of treatment in the subset of participants who have intraocular microfilariae just prior to treatment with IDA 2. To compare rates of ocular adverse events (any grade) by treatment group that occur within 3 months of treatment with IDA Efficacy 
 1. To compare the effect of three treatment regimens for killing adult female O. volvulus worms based on the percentage of all adult female worms in nodules that are alive 18 months after treatment with IDA 2. To compare the effects of three treatment regimens for complete clearance of microfilariae from the skin. 3, 12 and 18 months after treatment with IDA 3. To compare the effects of three treatment regimens for preventing reappearance of microfilariae in the skin at 12, and 18 months after treatment with IDA.
------------------------------	---

2 BACKGROUND INFORMATION AND SCIENTIFIC RATIONALE

2.1 Background

Ocular disease associated onchocerciasis and exacerbation with treatment

Onchocerciasis is caused by the filarial nematode *Onchocerca volvulus* and transmitted by the bite of *Simulium* blackflies that breed in rivers. Larval parasites (Mf) migrate through the skin and can cause severe skin and ocular diseases (“river blindness”). The World Health Organization (WHO) estimates that at least 25 million people are infected worldwide, affecting mainly 31 countries in sub-Saharan Africa, including Ghana ^{1, 2}. Onchocerciasis is the world’s second leading infectious cause of blindness. An estimated one million people have been blinded or have severe visual impairment due to onchocerciasis ^{1, 2}. Mass drug administration (MDA) with ivermectin for onchocerciasis has significantly reduced the burden of infection and associated ocular disease to the point where ocular disease is now uncommon in most endemic areas ^{2, 3}. Improved treatments that kill or sterilize adult *O. volvulus* worms would accelerate elimination of the infection.

2.2 Literature Review

Ocular pathology related to onchocerciasis was previously more common in savannah areas of West Africa and in Central America, and this has been attributed to various factors, such as localization of nodules in the upper part of the body, vector species, Mf burden, and parasite strains ^{4, 5}.

Onchocerciasis is a parasitic worm infection transmitted by *Simulium* black flies. The flies breed near rivers/streams, and biting rates are highest near the breeding sites. The infection is common in forested and savannah areas in West Africa that are drained by fast flowing rivers and streams.

Ocular pathology (including blindness) was previously more common in savannah areas. Reasons for this are not fully understood, but we provided two references in the text to demonstrate what is known ^{4, 5}.

The actual route of entry of Mf into the eyes is not known, but proposed routes include the sheaths of the posterior ciliary arteries and nerves, the blood stream, the bulbar conjunctiva with entry through the limbus, and along the orbital septum and the cheek ligaments ^{6, 7, 8}. The most common ocular lesion involves the cornea, that begins with “fluffy” or “snow-flake” stromal opacities (i.e., punctate keratitis), which later coalesce with fibrosis (i.e., sclerosing keratitis). The anterior chamber can be invaded by Mf, and death of Mf can be associated with uveitis with formation of synechiae, cataract and glaucoma. The lesions in the posterior segment of the eye include atrophy of the retinal pigment epithelium (RPE), choroidoretinal scarring, subretinal fibrosis and optical neuritis and post-neuritic optical atrophy which can be associated with permanent visual loss ^{9, 10}.

The main pathological changes seen in the posterior chamber of the eye are related to local invasion and host reactions to death of Mf within the retinal tissue. Some researchers have hypothesized that cross-reactive antibodies induced by *O. volvulus* antigens (Ov39) and the RPE antigen (hr44) may contribute to posterior segment diseases ^{11, 12, 13, 14, 15, 16}. Indeed there is evidence of persistent ocular deterioration in subjects even following clearance of Mf from the anterior chamber of the eye ¹⁷, or after years of repeated IVM treatment ¹⁸. Whether these late ocular changes are a) the result of autoimmune responses, b) persistence of Mf or their products in the posterior chamber, or c) a parasite-independent disease progression is unknown. This is partly due to limitations in technology available to assess the retina when these studies were performed. New methods are now available to better assess the posterior chamber of the eye. Such techniques have not been previously used to study ocular pathology in subjects with onchocerciasis (see below).

Onchocercal ocular disease has decreased dramatically with widespread use of IVM. Because IVM alone has no permanent effect on the adult worms and adult worms can live up to 15 years, the use of IVM alone for onchocerciasis elimination has only been successful in areas with low transmission, and/or in geographically isolated areas such as in the Americas ¹⁹, Senegal and Mali ²⁰ or Northern Sudan ²¹. However, there also examples where 15 or more rounds of IVM were not sufficient to interrupt transmission ^{22, 23, 24}. There is an urgent need to find new drugs or novel combinations of existing drugs that can partially or completely sterilize/kill adult worms for elimination of onchocerciasis in Africa to occur ^{25, 26}. Studies of new treatments should use the best available methods to assess potential ocular adverse events following treatment.

The prevalence of Mf in the eye is correlated with microfiladermia levels and overall community prevalence of onchocerciasis ^{6, 7, 8, 27}. Intraocular Mf are uncommon in persons who live in areas with microfiladermia rates below 20%, and they are uncommon in persons with <10 Mf/mg skin. Additionally, high intraocular Mf counts are not always associated with high rates of eye disease. For example, 44% of examined individuals in a hyper-endemic focus in Western Uganda had Mf in the anterior chamber, but sclerosing keratitis and vision loss were uncommon⁵.

Prior treatments for onchocerciasis using diethylcarbamazine and ivermectin

The use of DEC and its associated adverse events in individuals with heavy infections with onchocerciasis was recently reviewed by the study team²⁶. The discussion below summarizes some key points from that publication. Prior to 1987, an 8 to 14 day course of diethylcarbamazine (DEC) was commonly used to treat onchocerciasis. DEC was an effective microfilaricide, but it occasionally was associated with the development of severe inflammatory responses—both systemic and dermal—caused by the death of Mf. This is referred to as a Mazzotti reaction. DEC also caused adverse events in the eye, with punctate and sclerosing keratitis, limbitis, anterior uveitis, and chorioretinitis. It sometimes caused optic neuritis with edema and visual impairment in individuals with heavy *O. volvulus* infection who received high doses of the drug for prolonged periods^{9, 28}.

During the 1980's a single dose of IVM was shown to be more effective than DEC for clearing the Mf from the skin with minimal ocular adverse effects²⁹, and it has been the treatment of choice since that time. IVM reduces *O. volvulus* Mf numbers in skin within a few days with a nadir of skin Mf between 1 and 3 months post-treatment. Mf may reappear in the skin as early as 3 months post-treatment³⁰. Mf clearance from the eye following IVM treatment is slower by several months than clearance observed in the skin^{6, 31}. The nadir of Mf clearance from the anterior chamber of the eye starts 6 months post-treatment based on unpublished results from heavily infected subjects in the Volta region of Ghana with ocular Mf (Table 1), and that reduction persisted out to 18 months after treatment³².

Table 1. Kinetics of Mf clearance from the anterior chamber of the eye following IVM treatment

Visit (Days/months post IVM 150 mcg/kg treatment)	Subjects with ≥ 1 Mf in the anterior chamber of both eyes before and following a single dose of IVM n/N (%)
Day 0 (pretreatment)	205/205 (100)
Day 3	145/174 (83.3)
Day 4	21/23 (91.3)
Month 1	90/201 (44.8)
Month 6	14/200 (7.0)
Month 12	16/195 (8.2)
Month 18	13/160 (8.1)

The clearance of Mf from the posterior chamber of the eye is poorly understood because it is more difficult to visualize this part of the eye. Several studies have shown that anterior segment lesions such as punctate keratitis, sclerosing keratitis, iridocyclitis improved after IVM^{33, 34}, but there are conflicting data about the effectiveness of IVM for improving vision or preventing visual loss related to posterior segment lesions.

The [name] et al. review also discussed the possibility for re-introducing DEC in combination with ivermectin and albendazole, referred to as IDA for treatment of onchocerciasis²⁶. The reason for this is that IDA has been found to be much more efficacious for treatment of lymphatic filariasis (LF)³⁵. This study along with a large multicenter safety study (manuscript development in progress) resulted in the World Health Organization changing its guidelines to recommend IDA for LF outside Africa³⁶. Based on this recommendation Merck Sharp & Dohme Inc agreed to increase

their donation of ivermectin by 100 million doses per year for use of IDA in MDA programs for LF outside of sub-Saharan Africa³⁷. LF is often co-endemic with onchocerciasis in sub-Saharan Africa. This raises the important question of whether IDA can be safely used for LF elimination in coendemic areas. We hypothesize that IDA will be safe for use in persons with onchocerciasis if dermal and ocular Mf are cleared or greatly reduced by pretreatment with ivermectin alone

Many studies have examined Mf clearance from the skin after IVM treatment and these have been summarized in a meta-analysis³⁸. These results show microfilaridermia are reduced by half after 24 h, by 85% after 72 h, by 94% after 1 week, and by 98-99% after 1-2 months. Mf reappear in the skin as early as 3 months post-treatment³⁸.

Ocular Mf in the anterior chamber of the eye can be readily observed with a slit lamp. Using slit lamp examination Mf clearance from the eye following ivermectin treatment lags that observed in the skin by several months, but most treated subjects completely clear Mf from their eyes by three or six months after treatment^{6, 33, 34}. This was highlighted in a recent study where individuals with >10 Mf in the anterior chamber and treated with a single dose of 150 ug/kg of ivermectin and examined at 4 day, 1, 6, 12 and 18 months post-treatment show that Mf reached a nadir in mean Mf numbers in the anterior chamber at 6 months with little increase at 12 and 18 months³⁹. Mean percent reduction in Mf in the anterior chamber was 97±12%, N=74 at 12 months³⁹. Among the few individuals that failed to clear ocular Mf in anterior chamber, almost all ocular Mf were immobile and probably dead.

A few older studies describe lesions associated with Mf in the posterior segment of the eye^{9, 33, 40, 41}, which are thought to cause most of the irreversible causes of visual loss. These changes primarily involved optic nerve disease and choroido-retinal changes, particularly retinal atrophy. However, Mf were rarely observed in the posterior segment of eye, even among individuals with high levels of microfiladermia. Several studies have shown that IVM may improve anterior segment lesions such as punctate keratitis, sclerosing keratitis, iridocyclitis³³, but there are conflicting data about the effectiveness in preventing visual loss from posterior segment lesions¹⁸. The current study will examine whether IDA, which includes DEC, can be safely used following a pretreatment dose of IVM to reduce Mf in the eye.

2.3 Problem Statement

Better treatment is needed to eliminate Onchocerciasis

Programs for control of onchocerciasis through community directed treatment with IVM as a form of MDA have been in place for almost 30 years. IVM is effective for clearing Mf and it temporarily sterilizes adult female worms, but it is not a microfilaricide and does not kill adult worms. For that reason, MDA with ivermectin must be repeated for the reproductive life of the adult worms, which is 10-15 years. Thus, there is a widely recognized need for drug(s) that can kill or permanently sterilize adult worms. A new, safe, short-course treatment that kills or sterilizes adult worms would be a breakthrough that could accelerate onchocerciasis elimination in Africa.

The enhanced activity of IDA against filarial worms that cause LF suggests that this combination should be tested against *O. volvulus*. However, a single dose of IDA may be insufficient to kill/sterilize adult *O. volvulus*. Therefore, it is important to initially test the impact of a short multi-dose regimen of IDA. Three days of treatment would approach the practical limit for an MDA regimen.

Triple drug treatment for elimination of Lymphatic Filariasis in Africa

Recent studies have shown that a single co-administered dose of IVM, DEC and ALB (IDA) is far superior for long-term reduction and elimination of blood Mf of human lymphatic filariasis (LF) compared to the standard treatment of a) IVM and ALB or b) DEC and ALB, indicating permanent sterilization of adult worms. This combination therapy should require only one or two annual rounds of MDA to interrupt transmission (with high compliance) in areas with moderate endemicity, while five or more rounds are required with prior 2-drug regimens. WHO has recently recommended use of IDA for LF elimination in regions that are not coendemic for onchocerciasis or loiasis and that are not currently on track to eliminate LF by 2020 (e.g. Madagascar, Zimbabwe). However, these countries represent only 10% of the population at risk for LF in the AFRO region. If IDA can be safely used in persons with onchocerciasis after pretreatment with IVM, it could be very useful for eliminating LF in countries that are coendemic for LF and onchocerciasis even if the combination is not effective for killing or sterilizing adult *O. volvulus* worms. While this study is not powered to demonstrate safety of IDA in persons with onchocerciasis, it will provide preliminary safety data that could lead to larger safety studies later.

The WHO does not currently recommend use of IDA in areas with co-endemic LF and onchocerciasis. That is because one of the medicines in the IDA combination (diethylcarbamazine, also known as DEC) can cause severe/serious ocular adverse events in persons with high intensity infections with Mf in the eyes. Ivermectin pre-treatment (required for inclusion in this study) will reduce or completely clear Mf from the eyes of participants before they are treated with IDA in this study. Thus, pre-treatment should make it safe for participants to be treated with IDA. That would lead to accelerated elimination of LF in Africa, and IDA may also be better than currently available treatments used for elimination of onchocerciasis.

Gaps in knowledge about onchocercal eye disease

Although *O. volvulus* Mf can be readily observed in the anterior segment of eye using a slit lamp, it is challenging to visualize them in the posterior segment by previously used methods such as fundus photography, fluorescein angiography or indirect ophthalmoscopy. It is very uncommon for Mf to be in the posterior segment if the anterior chamber is clear. It is widely accepted among onchocerciasis researchers that the risk of ocular adverse events following DEC treatment is believed to be related to the number of Mf in the eye prior to treatment. Ophthalmologists believe that significant ocular adverse events (AEs) are very unlikely to occur if few Mf are present in the anterior chamber ([name], Department Chairman of Ophthalmology at Washington University in St. Louis; [name], onchocerciasis expert and Professor of Ophthalmology, University of Melbourne, Australia; [name], a retired Ghanaian ophthalmologist and former Director of the WHO Onchocerciasis Control Programme).

New technology to better understand onchocercal ocular disease

The methods currently available to evaluate ocular disease in patients with onchocerciasis include slit lamp, direct and indirect ophthalmoscopy, fundus photography, and fluorescein angiography. The latter test requires intravenous injection of a dye that sometimes causes acute adverse events (1 – 9%) that can include nausea, vomiting, allergic reactions, and (rarely) hypertensive crisis or myocardial infarction. Slit lamp examination is useful for demonstrating the presence of Mf in the anterior segment of the eye, including the cornea and anterior chamber, and in the vitreous, and for evaluating the presence and severity of intraocular lesions. Optical coherence tomography (OCT) is

the current method of choice for detailed assessment of the posterior segment and retina for many ocular diseases. It is a rapid, simple, precise and non-invasive imaging method that uses low intensity laser light to capture three-dimensional images of both the anterior and posterior segments of the eye with micrometer-resolution ⁴². OCT examinations are safe and they only require a few minutes. OCT has not been used previously in patients with onchocerciasis. It should allow examiners to visualize Mf in eye in the visual axis of the eye, particularly the posterior segment, and to evaluate retinal anatomy in a way that is superior to fluorescein angiography with no risk of adverse events.

OCT is not a new technology. It has been used to evaluate the posterior segment of the eye for more than 20 years, and several centers in Ghana have OCT machines. However, since most ophthalmological studies of onchocerciasis were performed prior to development of OCT, this will be the first study to use of OCT in patients with onchocerciasis. OCT is less invasive and provides a more detailed assessment of retinal anatomy than fluorescein angiography, which was used in past studies of posterior segment disease related to onchocerciasis. OCT is the state of the art, and it is appropriate that we use it in this study to carefully assess potential adverse events following treatment.

The slit lamp is better for assessing the anterior segment of the eye, and OCT is superior for the posterior segment. These are complementary tools, and both will be used in this study for every eye examination. Ocular exams will occur the day prior to treatment, on Day 3 after treatment (during the 7 day observation period), and on Day 7 of the observation period.

3 HYPOTHESES

1. Triple drug therapy with ivermectin, diethylcarbamazine and albendazole (IDA) (following ivermectin pretreatment) is more effective for killing or sterilizing adult female *O. volvulus* worms than ivermectin plus albendazole.
2. Triple drug therapy with ivermectin, diethylcarbamazine, and albendazole (following ivermectin pretreatment) is as safe as IVM/ALB alone in persons with onchocerciasis.

4 STUDY OBJECTIVES AND PURPOSE

This study will provide preliminary data on the safety of IDA treatment in persons with onchocerciasis when it is administered after pre-treatment with IVM to clear or greatly reduce microfilariae from the skin and eyes. Widespread use of IDA following IVM pretreatment (I/IDA) has the potential to greatly accelerate elimination of LF in African countries that are coendemic for LF and onchocerciasis.

Note that the sample sizes per treatment group in this study are not sufficient to conclusively demonstrate that IDA after IVM pretreatment is safe enough for widespread use in communities. Therefore, the safety study should be considered to be exploratory, and larger studies would be needed to formally establish safety of a pretreat/treat strategy with ivermectin followed by IDA (“I/IDA”). Having said that, a small exploratory safety study like this is an appropriate first step, because it should generate sufficient data to justify (or rule out) performance of a larger safety study later.

This study will also assess the efficacy of IDA for killing and sterilizing adult filarial worms. An improved macrofilaricidal treatment would be a major advance for the global program to eliminate onchocerciasis. Since the safety and efficacy objectives are both very important, we have included dual primary objectives for the study.

Primary Objectives:	
Safety: To compare rates and types of severe adverse events (grade 3 or higher) that occur within 7 days following 1 day or 3 days of treatment with triple drug treatment (“IDA” = DEC with ivermectin and albendazole) with the comparator regimen of 1 day of treatment with ivermectin and albendazole (IA) in persons with active Onchocerca volvulus infections after pretreatment with ivermectin alone.
 
Efficacy: To compare the effect of three treatment regimens (1 day of IDA, 3 days of IDA, or IA) for killing or sterilizing adult female O. volvulus worms based on the percentage of all adult female worms in nodules that are alive with embryos in the uterus 18 months after treatment.

Secondary Objectives:	
Safety:
 
 1. To compare rates of adverse events grade 3 or higher by treatment group that occur within 7 days of treatment in the subset of participants who have intraocular microfilariae just prior to treatment with IDA to those who do not have intraocular microfilariae 2. To compare rates of ocular adverse events (any grade) by treatment group that occur within 3 months of treatment with IDA 
Efficacy
 
 1. To compare the effect of three treatment regimens for killing adult female O. volvulus worms based on the percentage of all adult female worms in nodules that are alive 18 months after treatment. 2. To compare the effects of three treatment regimens for complete clearance of microfilariae from skin snips 3, 12 and 18 months after treatment with IDA. 3. To compare the effects of three treatment regimens for preventing reappearance of microfilariae in the skin at 12, and 18 months after treatment with IDA.

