4.4 Randomization

At least six months after treatment with ivermectin (-5.5 months or +12 months) in the preceding Part I trial, participants will first be split into two strata – those without ocular Mf detected six months after ivermectin pretreatment in the Part I preceding study *AND* without ocular Mf detected at baseline in the part II study will be in stratum 1. Those participants with ocular Mf detected 6 months after ivermectin pretreatment in the preceding study *OR* with ocular Mf detected at the baseline exam for this study will be in stratum 2. Stratum 1 will be enrolled first, followed by stratum 2. This is a safety precaution that will ensure that participants with *any* Mf in either eye 6 months after ivermectin pretreatment in the previous study will be the last to be dosed with combination drug treatments in this study. The decision to stratify so that persons who might be at higher risk are dosed last was based on recommendations from external expert reviewers of our grant proposal.

Members of each stratum will be evenly randomized into one of three treatment arms:

Stratum 1: Ocular Mf negative by slit lamp six months after ivermectin pretreatment (in Part I) AND ocular Mf negative by slit lamp at baseline enrollment

1. IVM + ALB - Single dose of oral IVM (150 µg/kg) plus ALB (400 mg) (IVM/ALB)
2. IDA x 1 dose - Single dose of oral IVM (150 µg/kg), DEC (6 mg/kg) and ALB (400 mg)
3. IDA x 3 doses -Once daily for 3 days oral IVM (150 µg/kg), DEC (6 mg/kg) and ALB (400 mg)

Stratum 2: Oular Mf positive 6 months after ivermectin pre-treatment (in Part I) **OR** ocular Mf positive at baseline enrollment (ocular Mf counts by slit lamp greater than 0 but < 5 in either eye)

1. IVM + ALB - Single dose of oral IVM (150 µg/kg) plus ALB (400 mg) (IVM/ALB)
2. IDA x 1 dose - Single dose of oral IVM (150 µg/kg), DEC (6 mg/kg) and ALB (400 mg)
3. IDA x 3 doses -Once daily for 3 days oral IVM (150 µg/kg), DEC (6 mg/kg) and ALB (400 mg)

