4.7 Participant Treatment

At baseline, participants will be given ivermectin (150 $\mu\text{g}/\text{kg}$) pretreatment. This pretreatment will be provided the participants' villages near their homes following their consenting to participate in the study. *Please note, *all participants* will be treated with ivermectin at baseline to ensure that they have low skin and ocular Mf counts at the time of enrollment. (This treatment is *in addition to* the pretreatment with ivermectin given in the Part I study).

After the baseline treatment with ivermectin alone, participants will be randomly assigned to one of the following treatment arms (all oral medications)*:

I. Ivermectin 150 $\mu\text{g}/\text{kg}$ plus albendazole (400 mg)

II. IDA single oral dose

- a. Ivermectin, 150 $\mu\text{g}/\text{kg}$

- b. Diethylcarbamazine citrate, 6 mg/kg
- c. Albendazole, 400 mg

III. IDA three one time daily oral doses

- a. Ivermectin, 150 μ g/kg
- b. Diethylcarbamazine citrate, 6 mg/kg
- c. Albendazole, 400 mg

Randomized treatment to one of the three treatment arms will occur in cohorts of up to 20 individuals. This is based on the project's capacity for transport, examination, and housing of participants. Initial participants will be individuals who had zero Mf in the eyes six months after pre-treatment with IVM in Part I and zero Mf in the eyes at baseline for Part II. If IDA proves safe in all of these participants,(i.e. if there are no serious or severe adverse events in *any* participant in the first 7 days) the study will continue with participants who had Mf in the anterior chamber in either eye six months after IVM pre-treatment in the Part I study or at the baseline exams for this study. Study investigators will monitor the safety of the participants in each treatment cohort for 7 days before dosing the next cohort, and they will suspend the study if any treatment-related serious or severe adverse events occur. If SAEs are reported, the DSMB will be asked to review the cases and to implement study stopping and pausing guidelines if the SAEs are found to be related to study treatments.

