7 SAFETY REPORTING AND SAFETY MONITORING

Most treatment related adverse events (cutaneous or ocular) result from the death of microfilariae in the skin and/or the eye are related to death of parasites and are not due to direct toxic effects of the drugs in humans. Other adverse events such as nausea and abdominal pain sometimes occur after treatment with IVM, ALB, or DEC. These may be related to local physical effects of the tablets or to effects of these drugs on intestinal worms. AEs related to death of *O. volvulus* Mf typically occur following the initial (first time) treatment when the burden of Mf in the skin and eye is greatest. These AEs typically start 1 or 2 days after treatment and they may occur up to 7 days after treatment. After treatment, participants will be assessed daily in the center for adverse events for 7 days before being discharged to their communities.

If participants develop severe AEs (grade 3, events that interfere with activities of daily living) or serious AEs for any reason after they return to the Kpassa area, they will be transported to Kpassa Health Centre, Nkwanta District Hospital, or UHAS School of Public Health Research Centre at Hohoe hospital for evaluation and management. SAEs will be reported to the Ghana Food and Drug Administration (FDA), UHAS Research Ethics Committee, Ghana Health Service Ethics Review Committee (GHS-ERC), to manufacturers of study medications, and to other institutional review boards per Good Clinical Practice (GCP) guidelines and timelines.

More detail on Safety Reporting can be found in the Safety Plan corresponding to this study.

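### Secondary safety objective 1 sets ocular-Mf-positive against Mf-negative participants, but read literally section 4.7 selects most of the Mf-negative side for zero events, and the subset is not the randomised stratum

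*Combined protocol and SAP*

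**What the plan says.** **Objective.** Section 4 (secondary safety objective 1) takes grade 3 or higher adverse events within 7 days, by treatment group, and compares participants "in the subset of participants who have intraocular microfilariae just prior to treatment with IDA to those who do not have intraocular microfilariae". The synopsis (section 1) states the same objective without an Mf-negative comparator: "To compare rates of adverse events grade 3 or higher by treatment group that occur within 7 days of treatment in the subset" who had ocular Mf just before IDA.

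**Dosing order.** Section 4.4: "Stratum 1 will be enrolled first, followed by stratum 2". Section 4.7 makes the move to stratum 2 conditional. The condition is "if there are no serious or severe adverse events in *any* participant in the first 7 days", applied to the participants with no ocular Mf; if it is met, "the study will continue with participants who had Mf in the anterior chamber in either eye six months after IVM pre-treatment", or who had Mf at the Part II baseline. Section 7 glosses severe as grade 3: "severe AEs (grade 3, events that interfere with activities of daily living". Section 4.7 adds, for the investigators and every cohort: "they will suspend the study if any treatment-related serious or severe adverse events occur".

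**Other continuation rules.** Section 7.6 has the DSMB make a go or no-go decision after stratum 1 and weigh stopping for a serious event attributable to IDA. Section 7.7 provides for a pause after any serious event and a restart after review.

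**Strata.** Under section 4.4, stratum 2 is anyone with ocular Mf at the Part I six-month examination or at the Part II baseline. Sections 4.1 and 4.7 give everyone a further ivermectin dose before randomised treatment.

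**Analysis.** Section 8.2 plans logistic regression for adverse event rates across arms and allows baseline Mf burden as a covariate. It names no analysis for this contrast.

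**The concern.** The condition for dosing stratum 2 uses the same event (severe, meaning grade 3) and the same 7 days as the objective. Under that condition the Mf-negative rate is largely selected to be zero, so it does not estimate the rate in Mf-negative people. The two groups are also treated in different calendar periods and were never randomised against each other.

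Separately, the objective classifies people by status just before treatment, after a second ivermectin dose, whereas even allocation is planned within strata that also use an earlier examination. Some of stratum 2 may have cleared by then, so the subset can be smaller than the stratum, and its balance across arms is left to chance.

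Residual ocular Mf is the risk factor behind the dosing order. Section 4 expects these data to help justify or rule out a larger safety study. A positive-versus-negative difference here could be read as evidence on that risk factor when part of it comes from the dosing rule.

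**Working it through.** **Inputs from the documents.** Enrolment up to 300, and at least 61 per arm (section 8.1). Even allocation to three arms (section 4.4). Ocular Mf after one ivermectin dose: 14/200 = 7.0% at month 6, 16/195 = 8.2% at month 12, 13/160 = 8.1% at month 18 (section 2.2, Table 1). The documents give no size for the subset and no expected grade 3 rate; event rates below are assumptions, shown over a range.

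**1. The plan's own figure.** For 30% versus 15%, two-sided 0.05 and 80% power, the two-proportion formula without continuity correction gives 121 worms per arm. Design effect 1 + 0.3 × (6 − 1) = 2.5. Then 121 × 2.5 / 6 = 50.4, so 51 subjects, as stated. 51 × 1.2 = 61.2 gives the stated 61, or 183 in all. This sizes the worm endpoint, not the ocular subset.

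**2. Size of the subset, if Table 1 applies.**
- 183 × 0.07 = 12.8, about 4 per arm.
- 300 × 0.07 = 21, or 7 per arm.
- 300 × 0.082 = 24.6, about 8 per arm.
- If the second dose clears half of the remainder (assumed): 300 × 0.035 = 10.5, about 3 or 4 per arm.

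Table 1 is an imperfect guide. Everyone in it had ocular Mf at the start, which may overstate; its heading refers to both eyes, which may understate.

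**3. Share of the comparator that is selected.** With 21 in stratum 2, stratum 1 has 279. If half of the 21 have cleared, the Mf-negative group is 279 + 10.5 = 289.5, of which 279 / 289.5 = 96% come from stratum 1. Those 279 have zero events whenever stratum 2 is dosed under section 4.7. The other 4% can have events.

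**4. How often stratum 2 would be dosed under a literal section 4.7.** P = (1 − p)^n.

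| True 7-day rate p | n = 279 | n = 170 (of 183) |
|---|---|---|
| 0.1% | 76% | 84% |
| 0.5% | 25% | 43% |
| 1% | 6% | 18% |
| 2% | 0.4% | 3% |

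**5. Effect on a test of positive versus negative.** Take 21 positives and 279 negatives with zero events. One event gives Fisher p = 21/300 = 0.07. Two events give (21 × 20)/(300 × 299) = 0.005. So two events suffice at 0.05. If both groups share the same true rate p, the chance of at least two in 21 is 1 − (1 − p)^21 − 21p(1 − p)^20:
- p = 2%: 6.5%, against 1.9% without the selection.
- p = 1%: 1.9%, against 1.3%.

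These are conditional on stratum 2 being dosed. Multiplying by the probabilities in step 4, the chance of both is 0.004 × 0.065, about 0.03%, at 2% and 0.06 × 0.019, about 0.1%, at 1%. They also ignore suspension after a first related event in stratum 2.

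**6. Precision inside the subset.** The two-sided 95% upper limit for 0/n is 1 − 0.025^(1/n): 60% for 0/4, 41% for 0/7, 16% for 0/21. Comparing two arms of 7, five events against none are needed for Fisher p ≤ 0.05.

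**The case against.** Several replies have force. The protocol calls the safety part exploratory and underpowered, and this is a secondary objective. Both statements of it already say by treatment group. The Figure 1 caption places the eye examination before randomisation, so an arm comparison within a subset defined by that examination remains a randomised one; only its size and balance are unprotected. Section 2.3 also ties risk to Mf in the eye before treatment, so the narrower subset has a clinical rationale. Fisher's test is not the planned analysis; with a zero cell, the logistic regression in section 8.2 would have no finite estimate for the contrast.

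These points limit the concern. The exploratory label excuses low power, but it does not make a comparator selected on the outcome interpretable.

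A reader might go further and infer that the comparison is settled in advance. The documents do not support that. Only the stratum 1 contribution is zero, and only under a literal section 4.7. The Mf-positive rate is free, cleared stratum 2 members count as negative and can have events, and sections 7.6 and 7.7 describe DSMB review and restart.

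A reader might also infer that the subset is nearly empty. Squaring 7% gives 1 or 2 of 300, but that assumes the second dose works as well in people the first dose did not clear. The documents do not say so.

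Finally, a reader might quote a large false-positive rate by assuming 60 positives and 240 negatives at a 2% rate: about 34%. Table 1 points to 21 to 25 positives, and at 2% a stratum 1 of 240 meets the condition with probability 0.98^240 = 0.8%.

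**Conclusion.** The point holds as one of design and wording, of moderate importance. If section 4.7 is applied as written, about 96% of the Mf-negative comparator (under the half-cleared assumption) has zero events by selection. Whatever rule is applied, the contrast is non-randomised and confounded with calendar time. The conditional false-positive chance is modest: 6.5% at an assumed 2% rate and 1.9% at 1%, in circumstances that arise 0.4% and 6% of the time. The main problem is therefore how to interpret the contrast; frequent false alarms are not expected.

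The subset and the randomised stratum differ by definition. At Table 1 prevalence the subset is about 4 to 8 per arm, fewer if the second dose clears more people, and a clean result in 7 people cannot exclude a rate of 41%. The synopsis and section 4 state different comparisons. Sections 4.7, 7.6 and 7.7 give different conditions for continuing; until they are reconciled, the reader cannot know how far the stratum 1 rate was conditioned.

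**What to change.** 1. In the synopsis and section 4, state one objective: compare grade 3 or higher adverse events within 7 days between IDA x1, IDA x3 and IVM/ALB within randomised stratum 2.
2. Report Mf-positive versus Mf-negative descriptively only, and state that the stratum 1 rate is conditioned on the section 4.7 rule if that rule was applied.
3. List participants with ocular Mf just before treatment by arm, with event counts and exact confidence intervals.
4. Reconcile sections 4.7, 7.6 and 7.7, and record which rule governed the move to stratum 2.
5. State which examination is the Part II baseline. Section 4.6 uses the Part I six-month examination, the Figure 1 caption places eye examinations after the second ivermectin dose, and section 2.3 places one on the day before treatment.

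The cost is wording in the objectives and analysis plan; no new data are needed. The downside is that stratum 2 includes some people who have since cleared, which may dilute an effect; the listing in item 3 covers this. The arm comparison will still be imprecise and should be presented as such.
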